8.2.2.2 Percent reduction in all type seizure days

Percent reduction in all other type seizure days from Baseline will be calculated in the same manner as percent reduction in POS frequency as described in Section 8.1.2. This variable will be summarized in the same manner as percent reduction in POS frequency.

8.2.2.3 Responder outcome for all type seizure days

Responder outcome for all other type seizure days will be derived in a manner similar to the responder outcome for POS frequency as described in Section 8.1.3. This variable will be summarized in the same manner as 50% responder outcome for POS frequency.

8.2.2.4 Specified month seizure freedom

Specified month seizure freedom for subjects in the PGS Efficacy Analysis Set will be derived in a manner similar to specified month seizure freedom for the POS Efficacy

Analysis Set as described in Section 8.2.1.1. This variable will be summarized in the same manner as specified month seizure freedom for subjects in the POS Efficacy Analysis Set.

8.2.3 QOLIE-31-P

The scoring algorithm for QOLIE-31-P is described in Section 13.1. QOLIE-31-P will be summarized for the POS and PGS Efficacy Analysis Sets. No summaries of QOLIE-31-P will be provided for subjects with ULD. QOLIE-31-P was to be assessed at Months 2, 6, 12, 18, and 24 during the first 2 years of the Evaluation Period for subjects from N01252 and N01254, and assessments at Months 3, 6, 12, 18, and 24 during the first 2 years of the Evaluation Period for subjects from N01114. Additionally, QOLIE-31-P was to be assessed at EDVs. The limited number of assessments obtained at Month 3 for N01114 will not be summarized but will be provided in subject data listings. Prior to Protocol Amendment 25, QOLIE-31-P may have been assessed for more than 2 years after study entry for some subjects. These additional assessments will not be summarized but will be provided in subject data listings.

Observed values for QOLIE-31-P total score and subscale scores for Seizure Worry, Daily Activities/Social Function, Energy/Fatigue, Emotional Well-Being, Cognitive Function, Medication Effects, Overall Quality of Life, and Health Status will be summarized for Months 2, 6, 12, 18, and 24 and Last Value for the Efficacy Analysis Sets for POS and PGS. For each time point, summary statistics will be presented for the baseline scores for subjects with a change from baseline at the time point in addition to summaries of the observed values and changes from baseline at each time point. Only subjects with a non-missing change from baseline will be summarized at each time point.

The above scores will be also summarized for the 6-Month, 12-Month, 18-Month, and 24-Month Study Visit Cohorts, including summaries of the baseline scores for all subjects within each study visit cohort and summaries of observed values and changes from baseline for each time point for each study visit cohort.

Similar summaries will be provided for QOLIE-31-P distress items Seizure Worry, Daily Activities/Social Function, Energy/Fatigue, Emotional Well-Being, Cognitive Function, Medication Effects, Overall Quality of Life. Only subjects with a non-missing change from baseline will be summarized at that time point.

The rankings of prioritization items (Seizure Worry, Daily Activities/Social Function, Energy/Fatigue, Emotional Well-Being, Cognitive Function, Medication Effects, and Overall Quality of Life) will be summarized at the same time points as above and for all subjects and by study visit cohort as defined above. Changes from baseline will not be summarized, and only the numbers of subjects and sample means will be presented.

8.2.4 EQ-5D

EQ-5D (EuroQol Group, 2000) will be summarized for the POS and PGS Efficacy Analysis Sets. No summaries of EQ-5D will be provided for subjects with ULD. EQ-5D was to be assessed at Months 2, 6, 12, 18, and 24 during the first 2 years of the Evaluation Period for subjects from N01252 and N01254. Additionally, QOLIE-31-P was to be assessed at EDVs.

EQ-5D was not routinely assessed for subjects from N01114. Prior to Protocol Amendment 25, EQ-5D may have been assessed for more than 2 years after study entry for some subjects. These additional assessments will not be summarized but will be provided in subject data listings.

EQ-5D dimensions will be summarized for Months 2, 6, 12, 18, and 24 and Last Value for the Efficacy Analysis Sets for POS and PGS. The number and percentage of subjects with each response will be summarized for each dimension and time point. Percentages will be relative to the number of subjects with a response to the dimension at that time point. Additionally, for each dimension and time point, the number and percentage of subjects with each response will be summarized for baseline for subjects with an observed response at that time point. Additionally, each dimension will be summarized for the 6-Month, 12-Month, 18-Month, and 24-Month Study Visit Cohorts, including summaries for baseline for all subjects within each cohort and summaries of observed responses for all time points for each cohort.

Observed values for the EQ-5D visual analog scale (VAS) score will be summarized for Months 2, 6, 12, 18, and 24 and Last Value for the Efficacy Analysis Sets for POS and PGS. For each time point, summary statistics will be presented for the baseline VAS score for subjects with a change from baseline at the time point in addition to summaries of the observed values and changes from baseline at each time point. Only subjects with a non-missing change from baseline will be summarized at each time point.

EQ-5D VAS score will also be summarized for the 6-Month, 12-Month, 18-Month, and 24-Month Study Visit Cohorts, including summaries of the baseline scores for all subjects within each study visit cohort and summaries of observed values and changes from baseline for each time point for each study visit cohort.

8.2.5 Direct cost parameters

Direct costs data are collected based on concurrent medical procedures, healthcare provider consultations not foreseen by protocol, hospital stays, and ER visits. All direct cost parameters will be not summarized but will be provided in subject data listings.

8.2.6 Indirect cost parameters

8.2.7 The number of school or working days lost will not be summarized but will be provided in subject data listings. Socio-professional data

Socio-professional data is collected at Month 12 and Month 24 and at EDVs. Prior to Protocol Amendment 25, socio-professional data may have been collected for more than 2 years after study entry for some subjects. These additional assessments will not be summarized but will be provided in subject data listings. Socio-professional data are not collected for subjects from N01114 and subjects with ULD.

9 PHARMACOKINETICS AND PHARMACODYNAMICS

Plasma samples for BRV and concomitant AEDs and antiepileptic drugs (AEDs) will no longer be obtained, as directed by the integrated protocol amendment 25. No summaries of

BRV or concomitant AED/AMD plasma levels will be provided; plasma levels will only be provided in subject data listings.

10 IMMUNOLOGICAL PROCEDURES

This section is not applicable for this study.

11 SAFETY ANALYSES

Safety is assessed with AEs, laboratory tests (blood chemistry, hematology, urinalysis, and pregnancy test), vital signs, body weight, ECGs, physical examination, neurological examination, mental status, and psychiatric status. Summary tables will be provided for AEs; blood chemistry, hematology, and urinalysis; vital signs; body weight; and ECGs. No summary tables will be provided for pregnancy testing, physical examination, neurological examination, mental status, or psychiatric status.

All safety summaries will be based on the Safety Analysis Set.

For subjects entering from N01315, their ongoing AEs will be transferred into N01125, and their safety assessments will be provided in subject data listings only, no summaries will be presented.

11.1 Extent of exposure

A daily dose will be calculated for each study day from the day of first dose of BRV to the day of last dose of BRV for the purposes of calculating modal dose. Daily dose will be calculated as the sum of the AM and PM dose for each day.

Modal daily doses will be calculated across all study days on or after the day of first dose of BRV and up to and including the day of last dose of BRV. Modal daily dose is the most frequently taken daily dose during this period. In the event of a tie, the modal dose will be set to the lower of the tied doses. Modal daily dose will be categorized as follows:

Category	Definition
5 mg/day	<20mg/day
20mg/day	≥20mg/day to <50mg/day
50mg/day	≥50mg/day to <100mg/day
100mg/day	≥100mg/day to <150mg/day
150mg/day	≥150mg/day to <200mg/day
200mg/day	≥200mg/day

Subject years of exposure will be calculated by summing the exposure duration in days for all subjects being summarized, and dividing the resulting value by 365.25.

Subject years of exposure will be presented overall and by modal dose for the Safety Analysis Set. The subject years of exposure presented by modal dose will be the total subject years of exposure of subjects with that modal dose.

The number and percentage of subjects exposed to BRV will be summarized overall and by modal dose category. The number and percentage of subjects in each Exposure Duration Cohort (≥ 3 months, ≥ 6 months, ≥ 12 months, and so forth) will be summarized.

The number and percentage of subjects within each modal dose category will be summarized for each Exposure Duration Cohort; percentages will be relative to the total number of subjects in each Exposure Duration Cohort.

In addition to the overall summaries of the above, the above will also be summarized by subgroup for region (North America, Europe [EU member states], Europe [non-EU member states], Asia/Pacific/Other), and by indication (Partial Onset Seizures, Primary Generalized Seizures, ULD).

11.2 Adverse events

11.2.1 Definition of treatment-emergent AE

AEs will be classified as either pre-study or treatment-emergent. Pre-study AEs are defined as AEs which had onset prior to the date of the first dose of BRV. TEAEs are defined as AEs that had onset on or after the day of first BRV dose. AEs with an incomplete onset date will be classified as TEAEs if the month and year of onset (when only the month and year are specified) is the same as the month and year of the first BRV dose or the year of onset (when only year is specified) is the same as the year of first BRV dose.

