10.2.17 Adverse Events

At Entry Visit, the Investigator will record all the adverse events that were still ongoing at the end of the previous study. From Entry Visit onwards, adverse events will be assessed at each visit and recorded in the CRF and in the source documents. The study participant will be given the opportunity to report AEs spontaneously. A general prompt will also be given to detect adverse events, e.g., “Did you notice anything unusual about your health (since your last visit)?” In addition, the Investigator should review any self-assessment procedures (e.g. daily record cards) used in the study.

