12.3.4 Rule for Repetition of an AE

An increase in the intensity of an AE should lead to the repetition of the AE reporting with:

- the outcome date of the first AE being the same as the start date of the repeated AE,
- the Investigator's original description of the AE being the same for the first and repeated AE, so that they code to the same dictionary term.

confidential information and ucb property

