2.2.1.1 Primary safety variables

- Occurrence of a treatment-emergent adverse event (TEAE)
- Withdrawal due to adverse event (AE)
- Occurrence of a serious adverse event (SAE)

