3.2 Analysis time points

3.2.1 First and last dose of BRV

Unless otherwise noted, all references to the first dose of BRV in this SAP refer to the first dose of BRV during N01125 (ie, not the first dose of BRV from the previous study in which subjects participated in prior to N01125). Unless otherwise noted, all references to the last known dose of BRV in this SAP refer to the last dose of BRV taken across any study periods (ie, the last dose of BRV across both the Evaluation and Down-Titration Periods).

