11.2.2 General summaries of TEAEs

Pre-treatment AEs will be provided in a subject data listing; no summaries of pre-treatment AEs are planned.

An overall summary of AEs will provide the overall number of TEAEs and the numbers and percentages of subjects with at least 1 TEAE, with a TEAE that led to permanent discontinuation of study drug, with a drug-related TEAE, with a severe TEAE, with a treatment-emergent SAE, and with a drug-related treatment-emergent SAE. The number and percentage of subjects who died will also be summarized. This summary will be provided for all subjects in the Safety Analysis Set and also by subgroup for geographic region and indication.

The following summaries of TEAEs will be provided by MedDRA SOC and PT. All summaries are for the combined Evaluation, Down-Titration, and Post-Treatment Periods unless otherwise indicated.

Overall Incidence Summaries

- Incidence of TEAEs
- Incidence of TEAEs by 3-month time interval
- Incidence of TEAEs by study period (Evaluation, Down-Titration, Post-Treatment)
- Incidence of TEAEs for TEAEs occurring in at least 5% of subjects

- Incidence of TEAEs by 3-month time intervals for TEAEs occurring in at least 5% of subjects overall
- Incidence of non-serious TEAEs occurring in at least 5% of subjects

The incidence of TEAEs occurring in at least 5% of subjects will be summarized overall as noted above and also by subgroup for geographic region, indication, and randomized treatment from the previous double-blind study.

A subject is included in a 3-month interval if the subject was receiving BRV at any time during that interval based on their duration of exposure to BRV (eg, a subject with exposure for 91 days is included in the time interval for Months 1-3 and Months 4-6). Summaries of AEs by 3-month intervals will include all subjects who are classified into each time interval as defined above. TEAEs which had onset prior to or on the date of the last dose of BRV are included in summaries by 3-month time intervals.

Maximum Intensity and Causality

- Incidence of TEAEs by maximum intensity
- Incidence of drug-related TEAEs

Serious Adverse Events

- Incidence of treatment-emergent SAEs

Discontinuations due to TEAE

- Incidence of TEAEs leading to permanent discontinuation of study drug

TEAEs of interest

AEs of interest will be identified based on MedDRA search criteria, which are documented outside of the SAP. The following summaries will be provided for AEs of interest:

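### An adverse event ongoing at entry that ends BRV treatment in N01125 without recorded worsening or recurrence is missing from the AE-discontinuation table, though withdrawal due to AE is a primary safety variable.

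*SAP*

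**What the plan says.** SAP 2.2.1.1 and Protocol 13.1.2.1 list three primary safety variables. Only the first, occurrence of a TEAE, refers to treatment emergence. The second ("Withdrawal due to adverse event (AE") and the third, occurrence of an SAE, have no condition on onset. Protocol 13.1.3 plans separate tables of AEs leading to withdrawal and of SAEs, again without that condition in the sentence.

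The SAP then narrows this in three steps:

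- SAP 3.2.1 fixes the reference date: "all references to the first dose of BRV in this SAP refer to the first dose of BRV during N01125".
- SAP 11.2.1 classes events by onset only: "Pre-study AEs are defined as AEs which had onset prior to the date of the first dose of BRV" and "TEAEs are defined as AEs that had onset on or after the day of first BRV dose". It has no clause for an event that later worsens, becomes serious or ends treatment.
- SAP 11.2.2 lists "Incidence of TEAEs leading to permanent discontinuation of study drug" and the incidence of treatment-emergent SAEs. The matching rows of the AE overview carry the same restriction. For the rest, "Pre-treatment AEs will be provided in a subject data listing; no summaries of pre-treatment AEs are planned".

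On data capture, Protocol 10.2.17 states: "At Entry Visit, the Investigator will record all the adverse events that were still ongoing at the end of the previous study". Protocol 12.3.2.2 defines the onset date as the date the AE started. Protocol 12.3.4 provides for a new record on worsening: "An increase in the intensity of an AE should lead to the repetition of the AE reporting with" a start date equal to the outcome date of the first record.

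**The concern.** The primary objective is long-term safety and tolerability. An AE that a subject carried in from the previous study and that finally makes the subject stop BRV is a tolerability failure under N01125 treatment. For subjects who entered directly or during down-titration of the previous study (SAP 3.2.3, categories 1 and 2), dosing generally continues without a break. For them the first N01125 dose is largely an administrative boundary.

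An onset-only rule suits TEAE incidence. For withdrawal, the event being counted is the stop, which happens in N01125 whatever the start date of the AE. Applying the TEAE filter to that variable can only remove subjects from the count. It also allows two tables in the same report to give different numbers of AE withdrawals, with nothing in the SAP to explain the difference.

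**Working it through.** The documents give no figure for this quantity, so there is none to reproduce. The check applies the SAP 11.2.1 onset rule, with the reporting rules in Protocol 12.3.1, 12.3.2.2 and 12.3.4, to each type of AE that is ongoing at entry.

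1. **Same intensity, no recurrence, leads to permanent discontinuation.** There is one record, with onset before the first N01125 dose, so it is pre-study. It is absent from the discontinuation table and the overview row. It is counted in disposition (SAP 5.1) if AE is the CRF reason.
2. **Intensity rises after the first dose, then leads to discontinuation or is serious.** A repeat record is made, starting at the worsening. That record is a TEAE and is kept.
3. **Recurs after entry.** Protocol 12.3.1 requires recurrences to be reported. The new episode has a new onset, so it is a TEAE and is kept.
4. **Becomes serious with no higher grade recorded**, for example hospitalization for an AE already rated severe. There is no repeat record, so it is pre-study and absent from the SAE table.
5. **Partial onset date** sharing the month and year of first dose, or the year if only the year is known. SAP 11.2.1 classes it as a TEAE, so it is kept.

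Only cases 1 and 4 are lost.

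**Size.** SAP 2.4 gives 859 enrolled, including 6 from N01315. SAP 3.5.1 excludes those 6 from the Safety Analysis Set.

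- Denominator: 859 − 6 = 853, an upper bound because it assumes that all were dosed.
- Each missed subject: 1 / 853 = 0.117 percentage points.

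The documents do not say how many subjects enter with an ongoing AE, or how many of those fall into case 1 or 4. As an assumption only, suppose 10% to 40% enter with an ongoing AE and 1% to 5% of those are lost:

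- Low end: 853 × 0.10 × 0.01 = 0.85, about 1 subject, or 0.1 percentage points.
- High end: 853 × 0.40 × 0.05 = 17.06, about 17 subjects, or 2.0 percentage points.

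**The case against.** The strongest case on the other side is that the plan already covers most of these events.

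- **Reporting rules.** Worsening and recurrence both produce a new record under Protocol 12.3.1 and 12.3.4, and the outcome category for worsening in 12.3.2.2 points to the same repetition rule. Those records are TEAEs. This stands, and it limits the point to AEs that persist with neither recorded.
- **Disposition.** SAP 5.1 counts discontinuations by CRF reason in the Safety Analysis Set, overall and by region and indication, whatever the AE onset. A reader might infer that these withdrawals vanish from the report; they do not. What is lost is the SOC/PT breakdown and the overview row. Disposition gives one collapsed AE category, so it does not replace that table, and the SAP plans no reconciliation.
- **SAEs.** A reader might infer that the SAE table is affected as much as the withdrawal table. The documents do not support that. The severe grade covers inability to carry out usual activities or definite clinical consequence, so a mild or moderate AE that becomes serious would usually move up a grade and be re-dated. What remains is mainly an AE already severe at entry. The exclusion for severe disorders that may affect safety (Protocol 8.2) and the expected-benefit criterion (8.1) make that uncommon. Deaths are counted without a TEAE condition.
- **Protocol wording.** The sentence in Protocol 13.1.3 on withdrawal and SAE tables follows one about TEAEs, so a TEAE restriction could be read into it. The variable definitions themselves contain none.
- **Direction.** The partial-date rule can bring in some AEs that truly began before the first dose, so the TEAE tables as a whole are not biased one way. The specific exclusion in cases 1 and 4 still only removes events.

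**Conclusion.** The point holds in a limited form. An AE ongoing at entry that leads to permanent discontinuation of BRV in N01125, with no recorded worsening or recurrence, is left out of the SOC/PT discontinuation table and the overview row, although the primary variable has no onset condition. The same happens, less often, to an ongoing AE that becomes serious with no higher grade recorded.

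The mechanism follows directly from the text. The size does not: only the 0.117 percentage points per subject, on at most 853, comes from the documents. The range of about 1 to 17 subjects rests wholly on assumed percentages. A claim that a substantial share of AE withdrawals or SAEs is missed would have no support in the documents. Nor do they show that the loss is greater among subjects previously on BRV than among those on placebo. TEAE incidence, the first primary variable, is not affected. The change is worth making because it is cheap and aligns the tables with the variables they are meant to report.

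**What to change.** In SAP 11.2.2:

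- **Discontinuation.** Base the SOC/PT table and the overview row on every AE whose action taken in N01125 was permanent discontinuation of BRV, whatever its onset date. Flag those with pre-study onset in a column or footnote. Protocol 12.3.2.2 already records this action for each AE, so no new data are needed.
- **Reconciliation.** Compare that total with the AE row of the disposition table and footnote any remaining difference. Some may be legitimate, because disposition uses the primary CRF reason.
- **SAEs.** Add to the SAE table and its overview row any AE with pre-study onset that was first reported as serious during N01125, and flag it. The AE items in Protocol 12.3.2.2 do not include the date an AE became serious, so these cases must be identified from the N01125 SAE reports.
- **TEAE incidence.** Leave it as defined.

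The cost is a short SAP text change, a pre-study-onset flag in the affected tables, and a check of flagged SAEs against SAE reports. Both rates may become slightly less favourable.

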
AMD=antiepileptic drug; AV=Additional Visit; CRF=Case Report Form; C-SSRS=Columbia-Suicide Severity Rating Scale; DTP=Down-Titration Phone Call; ECG=electrocardiogram; EDV=Early Discontinuation Visit; EV=Entry Visit; FEV=Full Evaluation Visit; FV=Final Visit; HADS=Hospital Anxiety and Depression Scale; IEC=Independent Ethics Committee; IRB=Institutional Review Board; MEV=Minimal Evaluation Visit; QOLIE=Patient Weighted Quality of Life in Epilepsy Questionnaire; ULD=Unverricht-Lundborg disease; YEV=Yearly Evaluation Visit

- (a) The following data (in parentheses) will be transferred electronically from the previous study and should not be recorded in the CRF: From the First Visit: General Medical and Procedure history, epilepsy history, disease history (for ULD subjects only), AED history and AMD history (for ULD subjects only).
- (b) From the last Evaluation Visit: vital signs, physical and neurological examinations, ECG, recording of seizures, laboratory assessment. Ongoing AE, procedures and medications at the end of previous study have to be recopied into the N01125 CRF appropriate sections (except subjects from N01315).
- (c) Height will only be recorded at Visit 1 (EV). Height will also be measured at each YEV and FV for subject still in growing period.
- (d) If an ECG has not been performed within the year, an ECG has to be scheduled once a year at the YEV. As well, an ECG shall be performed at the EDV and at the FV (if applicable). An ECG is mandatory at FV except if FV follows an EDV where ECG results were normal.
- (e) For subjects coming from study N01114 and for ULD subjects.
- (f) Procedures only performed during the first 2 years of subject participation in the study (eg. till last scheduled visit (YEV-Y3) or EDV/FV in case the subject discontinues participation within the first 2 years).
- (g) Laboratory assessment includes blood chemistry, hematology and urine analysis; where applicable (women with childbearing potential), a urine pregnancy test will be done.
- (h) Disease history, AMD history, concomitant AMD and concomitant nonAMD are collected only for ULD subjects.
- (i) Procedure not to be performed for ULD or N01315 subjects.
- (j) Down-Titration Phone call at the end of the Down-Titration Period is mandatory for all subjects in case the subjects discontinue from more than 20 mg/day brivaracetam. This phone call will also replace the previous Down-Titration Visit for ULD subjects.

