10.3 Study Conduct

Conduct of the visits is described in Flow chart (Section 4.1). Detailed description of assessments done during different type of visits is described in this section and in Procedures (Section 10.2).

The Entry Visit will be performed on the same day as the last visit of the previous study in which the subject was enrolled.

Should an interval become necessary between the last visit of the previous study and the entry visit in the present study, the Sponsor's Clinical study physician or representative should be contacted for agreement. The Adverse Events, medical procedures, non-antiepileptic/non-antimyoclonic and antiepileptic/antimyoclonic concomitant medication belonging to the interim period will be reported in the CRF, on specific pages.

Each visit will be planned within a "window" of ± 7 days from the previous visit. When possible, out-of-window visits should be rescheduled with respect to the Entry Visit.

At any time, the subject may have an additional study visit/phone call if the Investigator or the subject deems it necessary. All information, including reason for visit/phone call, any information on adverse events, etc., should be collected in the source documents and recorded in the appropriate section of the CRF.

For subjects coming from therapeutic exploratory studies during the early stage of development, visits will be organized on a monthly basis during the first 6 months, afterwards subjects' visits will be scheduled once every three months.

Coming from confirmatory studies at a later stage of the drug development, subjects will have monthly clinic visits during the first 3 months, afterwards subjects' visits will be scheduled on a three-monthly basis (Section 4.2). Subjects coming from N01315 will be scheduled on a three-monthly basis.

Note: Procedures performed within the first 2 years are not applicable to subjects coming from N01315.

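### The incomplete-date rule in SAP 11.2.1 can count an AE already known to be ongoing from the previous study as treatment-emergent

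*SAP*

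**What the plan says.** SAP 11.2.1 sorts AEs into pre-study and treatment-emergent by onset date: "Pre-study AEs are defined as AEs which had onset prior to the date of the first dose of BRV", and anything starting on or after the day of that dose is a TEAE. SAP 3.2.1 fixes the anchor: "all references to the first dose of BRV in this SAP refer to the first dose of BRV during N01125".

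For incomplete dates, SAP 11.2.1 states that "AEs with an incomplete onset date will be classified as TEAEs if the month and year of onset" coincide with those of the first dose, or, failing a month, that "the year of onset (when only year is specified) is the same as the year of first BRV dose". It attaches no other condition. Stop date, recording visit and carry-over status play no part.

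The protocol puts earlier events into the same CRF:

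- Section 10.2.17: "At Entry Visit, the Investigator will record all the adverse events that were still ongoing at the end of the previous study".
- Section 4.1, flowchart footnote (b): "Ongoing AE, procedures and medications at the end of previous study have to be recopied into the N01125 CRF appropriate sections", except for subjects from N01315.
- Section 10.3: if a gap between the studies is agreed with the sponsor, AEs "belonging to the interim period will be reported in the CRF, on specific pages".

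**The concern.** An AE recopied as ongoing at the end of the previous study began before N01125 treatment. Under Protocol 10.3 the Entry Visit normally falls on the day of the last previous-study visit, and Protocol 9.1.1.1 recommends the first intake that evening. A missing day or month therefore leaves the exact onset uncertain, but not its order relative to the first N01125 dose. The partial-date rule ignores that knowledge, so classification depends on how completely the date was written.

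Occurrence of a TEAE is the first primary safety variable (SAP 2.2.1.1). The same classification feeds the drug-related, severe, serious and discontinuation counts and the tables of TEAEs in at least 5% of subjects (SAP 11.2.2). A misclassified record would also drop out of the pre-treatment AE listing, where a reader would look for it.

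**Working it through.** The plan gives no figure on this point, so there is none to reproduce. The check has three parts.

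**1. The rule applied literally.** Take an invented first N01125 dose of 20 June 2008 and one AE recopied as ongoing.

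| Onset as written | Result under SAP 11.2.1 |
|---|---|
| 5 June 2008 | pre-study |
| June 2008 | TEAE |
| 2008 | TEAE |
| May 2008, or 2007 | not made a TEAE by the partial-date rule |

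The first three rows can be the same event.

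**2. Conditional share misclassified.** Assumptions: first-dose date uniform over a 365-day year; true onset uniform over the *T* days before first dose (lags of 1 to *T* days); AE still ongoing at entry; onset date incomplete. SAP 3.2.3 places the last previous-study visits at Week 12 or Week 16, hence *T* = 84 or 112. Values of 28 and 168 show the sensitivity.

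- Year only. An onset *L* days before first dose falls in the previous year for *L* of the 365 first-dose dates. Averaging over *L* = 1 to *T*, the share in the same year is 1 − (*T* + 1)/(2 × 365). For *T* = 84: 1 − 85/730 = 0.884. For *T* = 112: 1 − 113/730 = 0.845.
- Month and year. A first dose on day *d* of a month has *d* − 1 earlier days in that month. For *T* of at least 30, the year's total is 7 × 465 + 4 × 435 + 378 = 5,373, and the share is 5,373/(365 × *T*). For *T* = 84: 5,373/30,660 = 0.175. For *T* = 112: 5,373/40,880 = 0.131.

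| *T* (days) | Year only | Month and year |
|---|---|---|
| 28 | 96% | 52% (direct count) |
| 84 | 88% | 18% |
| 112 | 85% | 13% |
| 168 | 77% | 9% |

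An onset on the day of first dose itself is left out, because the full-date rule already counts it as a TEAE.

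**3. Effect on incidence.** SAP 2.4 gives 859 enrolled, 6 of them from N01315. SAP 3.5.1 excludes those 6 from the Safety Analysis Set, so the denominator is at most 859 − 6 = 853. Each subject whose only TEAE is a misclassified record adds 1/853 = 0.12 percentage points. For illustration only, 5, 10 or 20 such subjects would add 0.59, 1.17 or 2.34 points. The documents support no particular number.

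**The case against.** The strongest defence is that counting an ambiguous onset as treatment-emergent is a usual conservative default. The SAP is consistent here: it takes missing intensity as severe and missing relationship as drug-related (SAP 11.2.2). That stands for dates that are truly ambiguous. It does not cover a record whose onset before the first dose is already established.

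The triggering record should also be uncommon. Onset date is a required AE item (Protocol 12.3.2.2), source documents are verified in full against the CRF (Protocol 15.2), and a data review precedes analysis (Protocol 13.4). A year-only onset for an event ongoing at the end of a monitored study lasting a few months ought to be rare. This stands and limits the size. Subject-level incidence also moves only where the subject has no other TEAE, overall or within the same class or term.

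Some of these events may have begun on BRV, since subjects could have received it in the previous study. That is true, but the SAP chose the first N01125 dose as anchor, and by that anchor they are pre-study.

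A reader might infer that the misclassified events fall in Months 1-3 and inflate the interval against which later tolerability is read. The documents do not support this. SAP 3.2.2 gives no relative day to a partial date, SAP 3.2.5 defines the intervals by day number, and date imputation is mentioned only for medications (SAP 6.4).

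The interim-period pages matter only where a gap between studies occurred, and the documents do not say whether those pages feed the TEAE dataset.

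**Conclusion.** The point holds as a small defect of definition. For AEs recopied as ongoing from the previous study, the partial-date rule contradicts the pre-study definition in the same section, and nothing else screens these records out. The only exclusion by origin is that of the 6 N01315 subjects. AEs with complete dates are classified as the SAP intends.

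The error can only overstate TEAEs. Its absolute size is unknown and probably small, because the documents give no count of incomplete dates. The shares of 85% to 88% and 13% to 18% apply only to recopied AEs with a partial date and rest on the assumed even spread over 12 to 16 weeks; a 24-week window gives 77% and 9%. They should not be read as a proportion of all TEAEs, and they do not show that the primary result is materially inflated. The change is worth making because it is cheap, not because a large bias has been shown.

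**What to change.** Add to SAP 11.2.1 that the incomplete-date rule does not apply to:

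- an AE recorded at the Entry Visit as ongoing from the previous study;
- an AE recorded for the interim period, where such a gap occurred;
- an AE with a stop date before the first N01125 dose.

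These are pre-study unless a worsening is recorded as a repeated AE under Protocol 12.3.4. That section gives the repeated record its own start date, so genuine worsening in N01125 still counts. Report also how many AEs were classified by the partial-date rule, which would settle the size of the problem.

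The cost is one sentence and a small derivation step, with no new data collection. The documents describe no flag for recopied AEs. If none exists, they would have to be identified from Entry Visit records or matched to previous-study AE data, where subject numbers differ (Protocol 10.1).
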